6.1.1	Study Flow Chart and Plan	21
6.1.2	Procedures	21
6.1.3	Quality Control	24
6.2	Protection of Human Subjects.....	24
6.2.1	Subject Informed Consent (Primary Data Collection Only).....	25
6.2.2	Confidentiality of Study/Subject Data (Primary Data Collection Only)	25
6.3	Collection and Reporting of Adverse Events/Adverse Drug Reactions	25
6.3.1	Definition of Adverse Events (AE).....	25
6.3.2	Definition of Serious Adverse Events (SAE)	26
6.3.3	Definition of Adverse Drug Reactions (ADR)	Error! Bookmark not defined.
6.3.4	Collection of Adverse Events	Error! Bookmark not defined.
	Causality collection	Error! Bookmark not defined.
	Time period for collection of adverse events	Error! Bookmark not defined.
6.3.5	Reporting of Adverse Events	27
7.	LIST OF REFERENCES	29
8.	APPENDICES	30
9.	ATTACHMENTS	45
10.	SIGNATURES.....	46

LIST OF ABBREVIATIONS AND DEFINITION OF TERMS

Abbreviation or special term	Explanation
HRR	Homologous Recombination Repair
mCRPC	Metastatic Castrate Resistant Prostate Cancer
NCCN	National Comprehensive Cancer Network
PARP	Poly-ADP Ribose Polymerase
UCSD	University of California San Diego

RESPONSIBLE PARTIES

Name	Professional Title	Role in Study	Affiliation	Email Address
[name]	Associate [name]	UC San Diego	[contact]
[name]	Associate [name] Diego State University	[contact]
[name]	Staff Research Associate	Regulatory Contact	UC San Diego	[contact]
[name]	Clinical Trials Project Manager	Project Manager	UC San Diego	[contact]
TBD	Staff Research Associate	Study Coordinator	UC San Diego	

PROTOCOL SYNOPSIS

This is a pilot study to improve germline genetic testing for patients with aggressive prostate cancer as recommended by the updated guidelines by the National Cancer Comprehensive Network (NCCN) in 2018. Implementation of germline testing in men with prostate cancer has been low, in part due to the lack of resources to educate patients on germline testing including a growing national shortage of genetics counselors. Given limited genetic counseling services and a growing number of patients who qualify for germline testing, there has been interest in developing models to educate patients on germline testing in the clinic. In this study, consented patients will undergo a low-risk intervention of an educational session with a trained staff member on germline testing in prostate cancer and if agreeable, subsequent germline cancer genetic testing via a commercial lab test.

Background/Rationale: Germline testing is recommended for patients with high risk localized, locally advanced, and metastatic prostate cancer. Despite this recommendation, implementation of germline testing in prostate cancer has been suboptimal. This is due in part to a large number of patients who are eligible for testing and a national shortage of genetic counsellors. Given this, there is a need for novel strategies to engage oncology clinicians in germline testing and integrate germline testing into the clinic. Improving the rates of germline testing is vitally needed as pathogenic germline alterations can have therapeutic significance for a patient's prostate cancer and can have implications for family members in terms of their own cancer risk.

Objectives and Hypotheses: The primary objectives of this study are to both assess the feasibility of a patient educational program to improve germline genetic testing for eligible patients with prostate cancer and to assess the effectiveness of a patient educational program with regards to increasing germline genetic testing rate among adult prostate cancer patients who are recommended to receive germline testing per guidelines.

We hypothesize that the intervention will be feasible with successful recruitment of our target sample size. We additionally hypothesize that the rates of germline testing among patients recruited to the study will be higher than rates of testing among patients not enrolled in the study.

Methods:

Study design: This is a prospective single arm quality improvement initiative for the use of a standardized educational intervention on germline testing in prostate cancer to improve the rates of germline genetic testing among patients recommended for testing. Patients who consent to the study will undergo a one-on-one in-person education session regarding the rationale and the benefits/risks of germline testing. Following the educational session, if a patient wishes to proceed with testing, they will sign the standard consent to proceed with germline testing via a commercial assay.

Data Source(s): Patients with prostate cancer treated in the UCSD Genitourinary oncology clinics.

Study Population: Men with prostate cancer who meet the criteria for germline testing.

Exposure(s): Consented patients will undergo an in-clinic educational session on germline testing in prostate cancer with a trained educator.

Outcome(s): Assess the proportion of patients enrolled in the study who underwent germline testing to the proportion of patients who did not enroll in the study. Assess the effect of a patient educational program on increasing germline genetic testing rate among adult prostate cancer patients who are recommended to receive germline testing per NCCN guidelines. .

Sample Size Estimations: Target accrual is 50 patients in 12 months.

Statistical Analysis: For the primary endpoints of feasibility of implementing an educational intervention, this will be assessed by the accrual rate over 12 months. For the endpoint of efficacy of the intervention in improving rates of germline testing, the proportion of patients who undergo germline testing in this study will be compared to the proportion of patients who undergo germline testing who were eligible, but not enrolled into this study during the study time period.

AMENDMENT HISTORY

Date	Section of study protocol	Amendment or update	Reason
		N/A	

MILESTONES

Milestone	Planned date
Finalize survey instruments	July 2021
Finalize Redcap database along with CRFs	August 2021
Hiring of clinical research coordinator	August 2021
Completion of video	September 2021
Training of research coordinator	August- September 2021
Start of accrual	October 2021
6-month assessment of accrual	April 2022
Database lock	October 2022 (or sooner if 50 patients are accrued)
Analysis	November 2022
ASCO Abstract	January 2023
First Manuscript	March 2023

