The patient will then have an opportunity to ask questions. If a patient wishes to proceed with testing, they will sign the standard consent to proceed with germline testing and the patient's clinician will be notified of intent to proceed with germline testing. Patients can elect to decline testing, defer testing to a later time, or request referral to genetic counseling to discuss the testing. We will track patterns of patient decision making following the educational intervention. Upon a patient deciding to pursue testing, testing will consist of a prostate cancer germline panel with a commercially available blood or saliva-based assay. Following the educational intervention, the patient will be asked to complete a short patient education and satisfaction questionnaire (Appendix D). Upon receipt of the results, the coordinator will alert the patient's clinician, who will then share the results with the patient either in clinic or by phone. If the results show a

pathogenic germline mutation, the patient will be referred to see the UCSD cancer medical genetics clinic for consultation with a genetics counselor. Additionally, the patient can elect to see a genetics counselor independent of the test results once the test results are reviewed. If a patient pursues genetic testing, following receipt of results, the patient's clinicians will be asked to complete a short survey on to assess how the results of germline testing affected the patient's current and future management (appendix D). There will be capacity for patients to complete questionnaires electronically. Additionally, to systematically understand the scope of questions asked by patients which will provide opportunity to optimize the educational intervention, we will record the educational sessions.

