3.2 Study Population

The target population for this study is patients older than 18, with prostate cancer who meet the NCCN criteria for germline testing and who have not undergone prior germline testing.

Subjects will include those patients seen at a facility in the UCSD Health System. Genitourinary oncology clinics will be screened 1 week in advanced for eligible patients. Recruitment procedures will also involve the review of subject records by designated study personnel (e.g., investigators and/or study coordinators) in order to identify potentially eligible subjects. Since Protected Health Information (PHI) will be accessed via the hospital's medical record database and scheduling system (e.g., EPIC/IDX) *prior* to contacting the potential subject about the research study, we have been granted a partial waiver of HIPAA authorization for access to PHI for purposes of prescreening only.

For patients who are eligible for the trial, the investigator will approach the subject and offer participation in the trial. Standard HIPAA authorization to collect research data from the subject's medical record will be obtained at the time of informed consent. Given the COVID-19 pandemic, we are conducting sessions both in clinic and virtually. This will primarily occur via video chat or telephone. Given that this is a low-risk intervention of an educational session, we believe that virtual consenting is also appropriate here given the current pandemic.

For patients who decline the intervention or have not been approached at the time of analysis, these patients will be considered a separate cohort for comparison to the intervention cohort.

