3.5 Participant Follow-up

Patients will be followed for 24 months following the educational session. We will capture deferred decisions to pursue germline testing during the 24-month follow up period. Data on oncologic outcomes, prostate cancer management, and cancer surveillance will be obtained from the medical record.

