4.2 Outcomes

Primary Endpoints

1. The proportion of patients who undergo germline testing among those who are enrolled to the study compared to the proportion of patients who undergo germline testing who were eligible, but not enrolled into this study during the study time period
2. Feasibility of implementing an educational intervention for men with prostate cancer at risk of having a hereditary cancer syndrome. This will be assessed by:
 - Accrual rate by month.
 - Proportion of patients who consent to educational intervention among those who are approached (stratified by whether consent was performed in-person or virtually).

Secondary Endpoints

1. Patient understanding of germline testing before and after the education intervention based on questionnaire responses.
2. Patient-reported opinions on germline testing before and after intervention, and patient-reported satisfaction after educational intervention based on questionnaire responses.
3. Physician responses regarding how the germline testing result changed patient management.
4. Prevalence of pathogenic germline mutations among study patients who undergo germline testing.

Exploratory Endpoints

1. Clinical factors (patient and family history, disease characteristics, and outcomes) that are associated with the presence of a germline mutation in a cancer susceptibility gene.

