4.4 Statistical Analysis Plan

4.5 Statistical Methods – General Aspects

4.5.1 Primary Objective(s): Calculation of Epidemiological Measure(s) of Interest (e.g. descriptive statistics, hazard ratios, incidence rates, test/retest reliability)

Primary Endpoints

With regards to the primary endpoint, at the completion of the study, the proportion of patients who complete germline testing among all who are enrolled to the study will be computed. A sample size of 50 patients produces a two-sided 95% confidence interval on the proportion with a width ranging from 0.27 to 0.29 when the observed proportion ranging from 0.3 to 0.7. For proportions, 95% confidence intervals will be calculated using the exact method.

We will also compute the proportion of patients who completed germline testing for all eligible prostate cancer patients evaluated in clinic but not enrolled into this study during the study period. Characteristics between these two groups will be compared using Fisher's Exacts or Wilcoxon Rank Sum tests. The proportion of patients who underwent germline testing in the intervention vs non-intervention cohorts will be compared using Fisher's exact test.

4.5.2 Secondary Objective(s): Calculation of Epidemiological Measure(s) of Interest (e.g. hazard ratios, incidence rates, test/retest reliability)

Secondary endpoints including germline mutation frequency, patient understanding of germline testing, and medical management from germline testing will be described using descriptive statistics such as bar graphs, box plots, percentages, means and standard deviations, etc.

4.5.3 Exploratory Objective(s): Calculation of Epidemiological Measure(s) of Interest (e.g. hazard ratios, incidence rates, test/retest reliability)

- Associations between clinical factors and pathogenic germline alterations will be evaluated using Odds Ratio.
- Impact of germline testing on prostate cancer and cancer surveillance management will be qualitatively described.

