4.6 Bias

4.6.1 Methods to Minimize Bias

We aim to reduce bias through several methods including systematically screening medical oncology and urology clinics to identify eligible patients. The research coordinator will have a rotating schedule of clinics to screen to ensure systematic non-bias selection of eligible patients. Additionally, the intervention will be offered in multiple media modalities including in-person, video, and telephone to accommodate patient preferences. The intervention and video will be available in English and Spanish to further limit selection bias. Furthermore, there is capacity to perform the intervention in the clinic coinciding with the patients clinic appointment or at a separate time that is feasible for the patient.

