Potential to learn more about my cancer risk	
Potential to learn more about the cancer risk of my family	
Trust in my physician and their recommendation for genetic testing	
Other (please specify; not required)	

- Of the following listed factors, which would **most** influence you in a decision to **not** pursue genetic DNA testing in the care of your cancer? (**Rank answers in orders of preference from 1 to 5, 1= best describes, 5= least describes**)

	Rank (1 = best, 5 = worst)
Potential of DNA test results to be of no clinical value	
Potential of DNA test results to lead to health, life or disability insurance discrimination	

Concerns about the privacy and confidentiality of DNA test results	
Concerns about the impact a positive result would have on my family and relatives.	
Other (please specify; not required)	

Section D

For each statement, please select if you ‘Disagree Strongly’, ‘Disagree’, ‘Neither Agree or Disagree’, ‘Agree’ or ‘Agree Strongly’.

		Disagree strongly	Disagree	Neither Agree or Disagree	Agree	Agree Strongly
1.	The information presented in this session was informative .					
2.	The information presented in the session was confusing or difficult to understand .					
3.	The information presented in the session was distressing .					
4.	The information presented in the session was useful .					
5.	The information presented in the session answered all of my questions and concerns .					
6.	The session was the right length of time .					
1.	The pamphlet was helpful in explaining the concept of genetic testing.					

2. For question #6, if you answered **disagree to disagree strongly**, please tell us whether your education session was:
 - A) Too long
 - B) Too short
3. For question #7, if you answered **disagree to disagree strongly**, please tell us whether the pamphlet was:

- A) Too basic
- B) Too advanced
- C) Other (*please specify*): _____

4. At the end of this educational session, my decision on pursuing genetic testing is:

- A) I want to proceed with germline testing done today.
- B) I do not want to proceed with germline testing today.
- C) I would like to see a genetic counsellor to discuss this further.
- D) I am unsure and will decide at a later date.

If you have any other comments about the educational intervention, please feel free to share below:

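### The only listed database lock (October 2022 or sooner) falls before any man can complete 24-month follow-up, and the plan does not say by when a test must occur to count toward the primary proportion

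*Combined protocol and SAP*

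**What the plan says.** **Calendar.** The Milestones table plans accrual from October 2021 and one database lock, dated "October 2022 (or sooner if 50 patients are accrued". Analysis follows in November 2022, an abstract in January 2023 and a first manuscript in March 2023. The synopsis targets 50 patients in 12 months. Section 4.7 gives interim analyses as not applicable.

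**Follow-up.** Section 3.5 follows enrolled men for 24 months from the educational session and states: "We will capture deferred decisions to pursue germline testing during the 24-month follow up period". Deferral is an accepted choice. Section 3.1 says "Patients can elect to decline testing, defer testing to a later time, or request referral to genetic counseling to discuss the testing", and one answer in Appendix C is "I am unsure and will decide at a later date". Under 4.6.1 the session may coincide with the clinic appointment "or at a separate time that is feasible for the patient".

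**Primary proportion.** Section 4.5.1 says that "at the completion of the study, the proportion of patients who complete germline testing among all who are enrolled to the study will be computed". Section 4.2 sets this against the proportion tested among men "who were eligible, but not enrolled into this study during the study time period". Section 3.2 puts into the comparison group those who decline or "have not been approached at the time of analysis, these patients will be considered a separate cohort".

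**The concern.** The lock rule and the follow-up rule cannot both be carried out as a single plan. Deferred tests are to be captured for 24 months, but the only data cut listed comes well before that.

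The primary endpoint is exposed because nothing says which rule governs it. Study completion could mean the October 2022 lock or the end of 24-month follow-up, and the two can give different proportions. The denominator is all enrolled men, so a man who enrols just before the lock counts in full even if he has had almost no time to test. Non-enrolled men are counted over a study period that is not defined and have no start date of their own. The Fisher comparison in 4.5.1 therefore sets two proportions side by side with no common observation time.

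**Working it through.** **1. The plan's own figure.** Section 4.8 gives a 95% interval width of 0.27 to 0.29 for n = 50 and observed proportions of 0.3 to 0.7. The exact (Clopper-Pearson) width is 0.2675 at 15/50 and 35/50, and 0.2895 at 25/50. The figure is reproduced. It describes sampling precision only and does not bear on timing.

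**2. Calendar** (planned dates from Milestones; October 2021 = month 0).
- Lock: month 12 at the latest. Analysis: month 13. Abstract: month 15. First manuscript: month 17.
- Longest possible span before lock: 1 October 2021 to 31 October 2022 = 395 days, about 13 months.
- First possible completion of 24 months: 0 + 24 = month 24 (October 2023).
- Last completion, for a man enrolled in October 2022: 12 + 24 = month 36 (October 2024).
- Men able to complete 24 months by the lock: 0 of 50. All the listed outputs also come before month 24. A session held after consent starts the 24 months later still.

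**3. Which passage sets the time by which a test counts?**
- Enrolled men: 3.5 gives a 24-month period for deferred decisions, but 4.5.1 does not refer to it.
- Non-enrolled men: 4.1.2, 4.2 and 4.5.1 give no index date and no follow-up length.
- Meaning of tested: 4.2 speaks of undergoing testing and 4.5.1 of completing it. Neither says whether a sample taken or a result reported is meant.

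**4. Direction.** Let N(t) be the number of the 50 enrolled men tested by cut date t. N(t) cannot fall as t increases, so N(t)/50 at an early cut is at most its value at a later cut. Each test that falls after the cut is worth 1/50 = 2 percentage points. The comparison proportion is also cumulative over calendar time. Whether the difference grows or shrinks depends on which proportion rises more after the cut, and the documents give no figure for either.

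**5. How observation time depends on the lock (illustrative).** Assume uniform accrual of 50 men over A months and a lock g months after the last enrolment. Men with under T months = 50 × min(1, max(0, (T − g)/A)). Mean observation = A/2 + g.

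| Assumed case | A, g | Under 3 months | Under 6 months | Mean (months) |
|---|---|---|---|---|
| 50 by month 12, lock at once | 12, 0 | 12.5 | 25 | 6 |
| 50 by month 12, lock one month later | 12, 1 | 8.3 | 20.8 | 7 |
| 50 by month 6, lock at once | 6, 0 | 25 | 50 | 3 |
| 50 by month 6, lock kept at month 12 | 6, 6 | 0 | 0 | 9 |

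The last two rows have the same accrual. The difference comes wholly from how the early-lock clause is applied.

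**The case against.** **What stands against the point.** These are planned dates for a 50-man pilot. Calling the paper a first manuscript makes later reporting of 24-month data plausible, although no data cut for it is given. Appendix C offers testing on the day of the session, so the share of men affected may be small. The finding that 0 of 50 complete follow-up concerns the follow-up data and does not by itself show that the primary proportion is wrong. Accrual and consent, the feasibility measures, are untouched.

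**Stronger readings that the documents do not support.**
- A reader might infer that enrolled men have no per-patient period at all. Section 3.5 gives them one; what is missing is its link to the primary endpoint.
- A reader might infer that faster accrual must bring an earlier cut. The clause can equally be read as permitting an earlier lock without requiring it, and the last row of the table then applies.
- A reader might infer from 3.2 that an early lock also moves the comparison cohort. Section 3.2 ties membership to the time of analysis, and Milestones dates the analysis separately, in November 2022, without the early trigger.
- A reader might put a figure on the lost tests, or conclude that the comparison is biased against the intervention. The documents give no deferral rate, no time from session to test and no test turnaround, so neither follows.

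**Conclusion.** The concern holds and should be fixed. On the planned dates it is certain that no enrolled man can complete the 24 months in 3.5 before the only listed lock, and that no later lock is listed. It is equally clear that no passage says by when a test must occur to count toward the primary proportion in either cohort.

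The effect on the enrolled proportion is conditional. If the lock falls at or near the 50th enrolment, and some men would test after it, the proportion is lower than at a later cut. It cannot be higher. The observation times in the table rest on assumed uniform accrual and an assumed lock date. The number of tests lost, and the direction of any effect on the comparison, remain unknown.

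**What to change.** 1. **Milestones.** Add an accrual-closure line and move the 50-patient early trigger to it from the database lock.
2. **Section 4.5.1.** Count a man as tested if testing is done within one fixed window, W months, of his index date. Use the same W and the same meaning of done (sample taken or result reported) in both cohorts. The index date is consent for enrolled men, which keeps in the denominator a man who consents but has no session. For non-enrolled men it is the first eligible clinic visit in the study period while still untested. Set W before testing data are analysed, and make it long enough to include deferred tests and testing after counselling.
3. **Cohort entry and lock.** Close entry to both cohorts at accrual closure, align 3.2 with this, and lock when the last man in either cohort has completed W.
4. **Section 3.5.** Either add a later descriptive lock at 24 months (about October 2024 if accrual runs to October 2022) or amend 3.5, so that Milestones, 3.5 and 4.5.1 agree.

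**Cost.** The primary analysis moves later by W. With accrual to October 2022 and the planned one month from lock to analysis:
- W = 1: lock November, analysis December 2022, before the January 2023 abstract.
- W = 3: lock January, analysis February 2023, after the abstract.
- W = 6: lock April, analysis May 2023, after the March 2023 manuscript.

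There is a real trade-off. A short W keeps the abstract date but excludes later deferred tests, which are the ones at issue. With a longer W the January abstract may report only accrual and consent. Indexing on consent also adds a second time zero beside the session date used in 3.5. Each non-enrolled man needs an index date and chart review through W. No extra patients or study procedures are needed.
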